#### ***8.4 Treatment Administration***

Total cumulative dose, dose intensity and relative dose intensity, time on treatment, cycle delays and dose reductions will be described following standard tables detailed in Appendix I.

Total cumulative dose, expressed in mg, is the sum of all the study drug doses from the first cycle until last cycle, including the dose received in last cycle.

Patients will be considered to be on-treatment for the duration of their treatment and 30 days following the last treatment dose. If the patient starts any new antitumor therapy outside this clinical trial or dies within 30 days of last treatment dose, the date of administration of this new therapy or the date of death will be considered the date of treatment discontinuation.

However, as a convention, the duration of the last cycle is considered to be 21 days (instead of 30 days) for dose intensity calculation purposes.

Intended dose intensity (mg/m^2) is the planned dose per cycle divided by the planned number of weeks per cycle.

Absolute dose intensity (mg) is the actual cumulative dose divided by the number of weeks of treatment. Relative dose intensity (%) is the ratio of absolute dose intensity divided by the intended dose intensity.

The item of the case report form (CRF) «Infusion delayed: yes/no» will be used to calculate the delayed cycles. For those cycles considered as delayed by the investigator, the delay will be calculated as:

Delay: Date of current drug administration – Date of previous drug administration – 21.

The infusion of the first cycle will be excluded from all calculations regarding cycle delays and modifications.

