### 12.1 Extent of Exposure

Subgroup analysis will be performed according to starting dose (7 mg FD vs. 3.5 mg/m^2). The tables will be annotated by adding a letter as suffix.

The tables included in the subgroup analysis are the following:

Table 12.1.1.1 Number of cycles administered and dose intensity

Table 12.1.2.1.3 Number of patients and cycles with dosing delay according to relationship

Table 12.1.3.3 Number of patient and cycles with dose reduction according to relationship

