#### 12.1.1 Treatment Administration

Table 12.1.1.1 Number of cycles administered and dose intensity

No. of cycles administered per patient	N	%
1		
2		
3		
...		
Median (range)		
Time on treatment* (weeks)		
Median		
Range		
PM01183 cumulative dose (mg)		
Median		
Range		
PM01183 dose intensity (mg/wk)		
Median		
Range		
PM01183 relative dose intensity (%)		
Median		
Range		

(\*)Time on treatment: defined as last infusion date plus 30 days, or date of death or subsequent therapy (whichever comes first) minus first infusion date.

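### SAP 8.4 divides a dose intensity in mg by one labelled mg/m² with no BSA conversion; taken literally, relative dose intensity for the 3.5 mg/m² patients is inflated by a factor equal to BSA (capped at 2.0)

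*SAP*

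**What the plan says.** SAP section 8.4 (Treatment Administration) builds RDI in four steps:

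- Cumulative dose: "Total cumulative dose, expressed in mg, is the sum of all the study drug doses".
- Absolute dose intensity: "Absolute dose intensity (mg) is the actual cumulative dose divided by the number of weeks of treatment".
- Intended dose intensity: "Intended dose intensity (mg/m"², closing bracket (the quotation stops at the superscript), which "is the planned dose per cycle divided by the planned number of weeks per cycle".
- RDI: "Relative dose intensity (%) is the ratio of absolute dose intensity divided by the intended dose intensity".

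Table 12.1.1.1 (SAP 12.1.1) has rows for cumulative dose in mg, for "PM01183 dose intensity (mg/wk"), and for "PM01183 relative dose intensity" in percent. It has no footnote on BSA. SAP 12.1 adds: "Subgroup analysis will be performed according to starting dose", that is 7 mg flat dose against 3.5 mg/m², and lists Table 12.1.1.1 among the tables to be split.

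Protocol 5.2.1 sets the two regimens: 7.0 mg flat every three weeks under protocol versions 1.0 and 2.0, and 3.5 mg/m² every three weeks from version 3.0 onward, with BSA capped at 2.0 m² so that the dose does not exceed 7 mg. BSA for dosing follows each centre's own practice. In the SAP, BSA is a baseline descriptor (Dubois formula, section 8.3) and a model covariate (section 6.2.2); it is not linked to dose intensity.

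**The concern.** An intensity in mg/wk divided by one in mg/m²/wk has the unit m², so it is not a percentage. For patients dosed by BSA, the protocol states the planned dose in mg/m². A programmer who takes the planned dose from the protocol and the unit from the SAP label will therefore use 3.5/3 as the denominator, and the result is the true RDI multiplied by the patient's capped BSA. For flat-dose patients there is no planned dose per m², so the natural denominator is 7/3 mg/wk and the percentage is valid; only the label is wrong for them.

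RDI is meant to show what fraction of the planned dose was delivered. Under the literal reading, the RDI row cannot be compared across the two starting doses, and patients whose dose was really reduced can print above 100%.

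**Working it through.** The documents state no RDI figure to reproduce, so this is a unit check followed by direct arithmetic.

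**Inputs**
- Planned dose from protocol version 3.0: 3.5 mg/m² every 3 weeks (Protocol 5.2.1).
- Planned flat dose: 7.0 mg every 3 weeks (Protocol 5.2.1).
- Cap: BSA 2.0 m². Check: 3.5 × 2.0 = 7.0 mg, which agrees with the stated maximum.
- First reduction level for BSA dosing: 2.6 mg/m² (Protocol 5.2.3, Table 3).
- BSA: the documents give no distribution. Assumed range 1.3 to 2.0 m², constant over cycles. For orientation, Protocol 1.2.1.2 treats 7.0 mg flat as equivalent to 4.0 mg/m², which implies 7.0/4.0 = 1.75 m².

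**Formulas**, with b = min(BSA, 2.0)
- Absolute intensity = (sum of mg/m² doses given × b) / weeks, in mg/wk.
- Literal RDI = absolute intensity / (3.5/3).
- Same-unit RDI = absolute intensity / (3.5 × b/3).
- Literal RDI / same-unit RDI = b.

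**Patient treated exactly to plan at 3.5 mg/m²**

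| BSA (m²) | Dose (mg) | mg/wk | Literal RDI | Same-unit RDI |
|---|---|---|---|---|
| 1.3 | 4.55 | 1.517 | 130% | 100% |
| 1.5 | 5.25 | 1.750 | 150% | 100% |
| 1.7 | 5.95 | 1.983 | 170% | 100% |
| 2.0 or above | 7.00 | 2.333 | 200% | 100% |

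At the implied 1.75 m² the literal value is 175%. A flat-dose patient treated to plan has (7/3)/(7/3) = 100%.

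**How far a shortfall can be hidden.** Literal RDI stays at or above 100% until true RDI falls below 1/b: 76.9% at 1.3 m², 66.7% at 1.5, 58.8% at 1.7 and 50.0% at 2.0.

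**Patient with reductions.** Four on-time cycles (12 weeks), the first at 3.5 and the next three at 2.6 mg/m²:
- True RDI = (3.5 + 3 × 2.6)/(4 × 3.5) = 11.3/14 = 80.7%.
- Literal at 1.3 m²: 11.3 × 1.3 = 14.69 mg; 14.69/12 = 1.2242; divided by 3.5/3 = 104.9%.
- Literal at 1.7 m²: 19.21/12 = 1.6008; 137.2%.
- Literal at 2.0 m²: 22.60/12 = 1.8833; 161.4%.

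**The case against.** The strongest reply is that the mg/m² label is a slip and nobody would compute the ratio this way. The SAP asks for a percentage, which the literal ratio cannot be. The words of the definition speak of planned dose per cycle and do not say per m²; only the bracketed unit does. The bracketed units are loose anyway: both leave out the week, and the table prints mg/wk where section 8.4 has mg. The label must also be set aside for flat-dose patients, so the simplest course is to set it aside throughout. The version history lists no change to section 8.4, so the label may predate BSA dosing. Protocol 5.2.1 already turns the planned dose into a capped amount in mg for each patient. Finally, reductions and delays have their own tables and listings, and a group with RDI near 170% would be noticed.

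Much of this stands. The percent unit does favour a per-patient mg denominator, and under that reading RDI is correct. The version-history argument is an inference; if it is right, it shows that the definition was not revisited when a second dosing unit was introduced. The two regimens also differ in a relevant way: the label cannot be followed for flat dosing, because no planned mg/m² dose exists, but it can be followed for BSA dosing, because the protocol states one. The label is wrong on either reading, and a correct table should not depend on the programmer disregarding the stated unit or on someone spotting an odd result.

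**Conclusion.** The concern holds, as a minor point. Followed with its own units and the protocol's planned dose, the SAP definition overstates RDI in the 3.5 mg/m² patients by a factor of min(BSA, 2.0). The mismatch of units and the absence of any conversion are certain from the text. The inflation is conditional on the literal reading, and the figures of 130% to 200% rest on the assumed BSA range. The factor is exactly BSA only if dosing BSA is constant; otherwise it is a dose-weighted mean.

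The effect is confined to the RDI row of Table 12.1.1.1 and its split by starting dose. Cycles, time on treatment, cumulative dose, mg/wk, delays, reductions and all efficacy analyses are unchanged.

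**What to change.** In SAP 8.4, define intended dose intensity for each patient in mg/wk from the protocol's own planned starting dose:

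- flat dosing: 7 mg / 3 weeks;
- BSA dosing: 3.5 mg/m² × min(BSA, 2.0 m²) / 3 weeks.

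Then set RDI = absolute (mg/wk) / intended (mg/wk) × 100, and correct both unit labels to mg/wk. Add one sentence naming the BSA: the value used for dosing if it is recorded (stating which cycle's value applies), otherwise the baseline Dubois value from SAP 8.3. Note that the fallback may differ from the dosing BSA, because centres use their own method, so a patient treated to plan may then not read exactly 100%.

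The cost is one definition sentence, two labels and one sentence on BSA, with no new table. Baseline weight and height are on the CRF (SAP 8.3). The protocol lists BSA among the clinical assessments (Table 5, footnote 1) but does not say that it is captured on the CRF, so that needs checking.

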### ***8.5 Subsequent Therapy***

A table summarizing the subsequent therapies received after treatment discontinuation will be shown.

### ***8.6 Pharmacokinetic Analysis***

This analysis will be detailed in a separate document.

### ***8.7 Pharmacogenomic Analysis***

This analysis will be detailed in a separate document.

### ***8.8 Imputation of Incomplete Dates***

The dates of certain historical or current clinical activities are key component for statistical analysis. An incomplete date results from a missing day, month or year; in that case, the missing figure can be imputed allowing for the calculation of variables, such duration and time to certain event. However, when all of them, day, month and year, are missing no imputation will be done.

#### ***Before registration***

If the day of a month is unknown, then the imputed day will be the 15th of the month; if the month is also unknown, then the imputed date will be the 1st of July. This assumption will only be valid if the imputed date occurs earlier than the first dose administration date; otherwise the imputed date will be the first day of the first dose administration month date (i.e. 01/ first dose administration month date/year).

#### ***Between treatment start and end of treatment***

All date variables during treatment where information is needed and is not fully available, for example adverse events or concomitant medications, will be subject of imputation by means of SAS programming. If the day of a date is unknown then the imputed day will be 1, if the month and/or year is also unknown then the imputed date will 1/January (this assumption will be valid if the imputed date is not earlier than the treatment start date; otherwise, the imputed date will be the treatment start date).

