5.2. ADMINISTRATION OF STUDY MEDICATIONS

5.2.1. Route of administration, starting dose, and schedule

Patients included under protocol versions 1.0 and 2.0 will receive PM01183 i.v. as a one-hour infusion on Day 1 q3wk at a starting dose of 7.0 mg FD (three weeks = one treatment cycle).

Patients included from protocol version 3.0 onward (after implementation of amendment no. 2) will receive PM01183 i.v. as a one-hour infusion on Day 1 q3wk at a starting dose of 3.5 mg/m² (three weeks = one treatment cycle). Dose will be capped at BSA of 2.0 m² (i.e., dose will not exceed 7 mg). BSA will be calculated according to standard practice at each center.

PM01183 will be administered over a minimum total volume of 100 ml of solution for infusion (either on 5% glucose or 0.9% sodium chloride) through a central catheter or over a minimum total volume of 250 ml if through a peripheral line, always over one hour at a fixed infusion rate.

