## 12.2.2 Display of Adverse Events

Table 12.2.2.1 Summary of AEs.

Category	N	%
Patients with at least one AE regardless relationship		
Any treatment-related AE		
Any grade 3/4 AE		
Any grade 3/4 treatment-related AE		
Any SAE in DB		
Any treatment-related SAE		
Any grade 3/4 SAE		
Any grade 3/4 treatment-related SAE		
AEs leading to death		
AEs treatment-related leading to death		
AEs leading to dose delay		
AEs leading to dose reduction		
AEs leading to treatment discontinuation		
AEs treatment-related leading to treatment discontinuation		

Table 12.2.2.2 Treatment-related AEs. Worst grade by patient

SOC	Preferred Term	Grade 1		...	Grade 4		All*	
		N	%		N	%	N	%
Blood and lymphatic system disorders	Anemia NOS							
	...							
	...							
Cardiac disorders	Arrhythmia NOS							
	...							

(\*) Any grade

Table 12.2.2.3 Treatment-related AEs. Worst grade by cycle

SOC	Preferred Term	Grade 1		...	Grade 4		All*	
		N	%		N	%	N	%
Blood and lymphatic system disorders	Anemia NOS							
	...							
	...							
Cardiac disorders	Arrhythmia NOS							
	...							

\* Any grade

Table 12.2.2.4 Adverse Events regardless of relationship. Worst grade by patient

SOC	Preferred Term	Grade 1		...	Grade 4		All*	
		N	%		N	%	N	%
Blood and lymphatic system disorders	Anemia NOS							
	...							
	...							
Cardiac disorders	Arrhythmia NOS							
	...							

(\*) Any grade

Table 12.2.2.5 Adverse Events regardless of relationship. Worst grade by cycle

SOC	Preferred Term	Grade 1		...	Grade 4		All*	
		N	%		N	%	N	%
Blood and lymphatic system disorders	Anemia NOS							
	...							
	...							
Cardiac disorders	Arrhythmia NOS							
	...							

(\*) Any grade

Listing 12.2.2.6 Treatment-related grade 3-4 AEs. Worst grade per patient

Patient id.	SOC Name	Preferred term	Grade

Listing 12.2.2.7 Treatment-related grade 3-4 AEs. Worst grade by cycle

Patient id.	Cycle	SOC Name	Preferred term	Grade

Listing 12.2.2.8 Adverse Events grade 3-4 regardless of relationship. Worst grade per patient

Patient id.	SOC Name	Preferred term	Grade

Listing 12.2.2.9 Adverse Events grade 3-4 regardless of relationship. Worst grade by cycle

Patient id.	Cycle	SOC Name	Preferred term	Grade

Table 12.2.2.10 Treatment-related SAEs. Worst grade by patient

SOC	Preferred Term	Grade 1		...	Grade 4		All*	
		N	%		N	%	N	%
Blood and lymphatic system disorders	Anemia NOS							
	...							
	...							
Cardiac disorders	Arrhythmia NOS							
	...							

(\*) Any grade

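### The on-treatment date rule in SAP 8.8 treats start and end dates alike, so an end date with a missing day can be imputed before a known onset

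*SAP*

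**What the plan says.** SAP 8.8 (Imputation of Incomplete Dates) explains that a missing date component can be filled in, "allowing for the calculation of variables, such duration and time to certain event". It then gives separate rules for three periods. The middle one, for the time between treatment start and end of treatment, covers "All date variables during treatment where information is needed and is not fully available, for example adverse events or concomitant medications". Under it:

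- Day missing: "If the day of a date is unknown then the imputed day will be 1".
- Month or year missing as well: "if the month and/or year is also unknown then the imputed date will 1/January".
- Guard: "this assumption will be valid if the imputed date is not earlier than the treatment start date". Where that condition fails, the first day of treatment is used instead.

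Adverse events and concomitant medications each have a start and an end date. The rule does not separate the two, and neither document requires an imputed end date to fall on or after the start of the same event.

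These outputs use or show such dates:

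- Listing 10.2.4, the listing in 12.1.2.3 and Listing 12.1.3.5 (AEs leading to discontinuation, delay and reduction) show onset and resolved dates side by side.
- Listing 12.6.4 shows G-CSF start and end dates.
- Tables 12.4.4.13 and 12.4.4.14 split the neutrophil time course by G-CSF use and by cycle.
- AE worst grade is tabulated per cycle, for example in "Table 12.2.2.3 Treatment-related AEs. Worst grade by cycle".

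**The concern.** Imputing to the 1st is a reasonable convention for a start date: it is early, and the floor keeps it within treatment. For an end date it works in the wrong direction. It gives the earliest possible day in the month, although the event is known to have ended no earlier than it began. If onset is known and lies later in that month, the record acquires a negative duration.

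This is a rule that is stated and gives an impossible value. It is not a gap that a programmer would notice and fill. Followed literally, it puts onset and resolution in the wrong order wherever imputed dates are displayed, and it corrupts any duration calculated from them. It could also misclassify G-CSF exposure in a cycle if exposure is worked out from start and end dates. A secondary question is whether moving an onset back to the 1st places the event in the wrong cycle.

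**Working it through.** The SAP states no figure for this rule, so there is none to reproduce. The check applies the rule as written.

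**Rule.** With month and year known, imputed date = the later of (1st of the month, treatment start date).

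**Worked examples.** Treatment starts 2 March 2015. Cycles last 21 days (Protocol 5.2.1: "three weeks = one treatment cycle"), so cycle 2 starts 23 March and cycle 3 starts 13 April.

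1. An AE runs from 20 to 27 April and the end day is missing. Imputed end = 1 April; duration = 1 − 20 = −19 days.
2. An AE starts 12 March and ends in March, end day missing. The floor applies: imputed end = 2 March; duration = 2 − 12 = −10 days. The floor does not prevent the error.
3. An AE ends in 2015 with the month also missing. Imputed end = 2 March 2015 (the floor), which is before any onset after that day.
4. The AE in example 1 has its onset day missing instead. Imputed onset = 1 April, in cycle 2; the true cycle is 3.
5. Both days are missing in the same month. Both become the same date and the duration is 0, not negative.

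**How often the imputed end precedes onset.** Assumptions: end day missing; onset known and spread evenly over n cycles of 21 days; no cycle delays; average month 30.4 days. An event lasting D days ends in its onset month, with onset after the 1st, on (30.4 − D − 1) of 30.4 onset days. Onset on the treatment start date itself is safe, which removes 1 day in 21n:

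P ≈ [(30.4 − D − 1) / 30.4] × [1 − 1/(21n)]

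| D (days) | First factor | n = 2 (× 41/42) | n = 8 (× 167/168) | Day-by-day enumeration, n = 2 to 8 |
|---|---|---|---|---|
| 3 | 26.4/30.4 = 0.868 | 0.848 | 0.863 | 0.848–0.863 |
| 7 | 22.4/30.4 = 0.737 | 0.719 | 0.732 | 0.719–0.733 |
| 14 | 15.4/30.4 = 0.507 | 0.495 | 0.504 | 0.495–0.504 |
| 21 | 8.4/30.4 = 0.276 | 0.270 | 0.275 | 0.270–0.276 |

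The last column enumerates every treatment start day in 2013–2015 and every onset day. It agrees with the formula to within 0.001.

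The short durations are relevant here. Protocol 1.2.1.2 reports that neutropenia at the recommended dose lasted a median of three days, and Protocol 5.2.3 describes G-CSF prophylaxis over five consecutive days.

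**How often an onset with a missing day moves to an earlier cycle.** This applies only if cycle is derived from the imputed onset. An onset k days into its cycle (k = 0 to 20, mean 10) moves back s days, with s evenly spread over 0 to 29.4. It leaves its cycle when s > k:

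P(cycle 2 or later) ≈ (30.4 − 1 − 10) / 30.4 = 0.638 (enumeration: 0.638–0.639)

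Cycle 1 onsets cannot move because of the floor. Over all cycles the figure is therefore 0.639 × (n − 1)/n: 0.32 for n = 2, 0.48 for n = 4, 0.53 for n = 6 and 0.56 for n = 8.

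**What cannot be computed.** The documents do not say how many on-treatment dates are incomplete. Every percentage above is per affected record.

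**The case against.** The best defence is that little in the plan depends on these dates. The SAP has no table of AE duration or G-CSF duration. The AE tables are counts by worst grade, G-CSF appears as a listing, a count and a yes/no split, and the tabulated durations are laboratory recovery times, which rest on sample dates. The rule is also limited to dates where information is needed, so some end dates may never be imputed, and the SAP does not say whether listings print collected or imputed dates. All of this stands and keeps the point small. It does not make the rule right: SAP 8.8 gives the calculation of durations as a purpose of imputation and names adverse events and concomitant medications as covered.

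Three stronger readings are tempting, and the documents do not support them.

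- **The by-cycle AE tables will be wrong.** This needs cycle to be derived from the imputed onset, which the SAP does not say. Several listings carry cycle as a column of its own, which is compatible with a CRF field.
- **Most onsets with a missing day change cycle.** A figure near 64% applies to cycle 2 or later only. Over all cycles the treatment-start floor brings it to 32–56%.
- **A death within 30 days of the last dose could be dated before the last infusion.** Such a death is itself the end-of-treatment date (Protocol 6.2). The next rule in SAP 8.8, After end of treatment, is written for DR, PFS and OS and requires an imputed date to be later than the last administration. Its fallback of last administration plus 21 days lies inside the 30-day window. The better reading is that this guard covers such deaths.

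**Conclusion.** The point holds for end dates. Applied literally, the on-treatment rule gives an end before onset whenever the end day is missing, the end falls in the month of a known onset, and that onset is neither the 1st nor the treatment start date. Nothing elsewhere in the protocol or SAP corrects it. The likelihood per affected record falls as events get longer, as tabulated above; those figures assume evenly spread onsets and no cycle delays.

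The reach is limited to the AE and G-CSF listings that show both dates, any duration computed under SAP 8.8, and the G-CSF split in the neutrophil tables if it is derived from dates. The move to an earlier cycle is conditional and secondary. The primary ORR analysis is untouched. This is a minor correction, worth making because the rule as written is wrong and easy to repair.

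**What to change.** Split the on-treatment rule in SAP 8.8:

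- **Start dates:** keep the 1st of the month (1 January if the month is missing), floored at treatment start.
- **End dates:** use the last day of the month (31 December if the month is missing), capped at death, last contact or clinical cut-off, and never earlier than the event's own start date, recorded or imputed. Do not cap at end of treatment, because Protocol 6.8 and 11.2.1 follow related AEs beyond it.
- **Cycle:** assign it from the CRF cycle field where one is recorded. State that it is derived from the date only where no such field exists; in those records some movement to an earlier cycle remains.
- **Deaths:** add one line stating that the last-administration guard in the After end of treatment rule applies to deaths within 30 days of the last dose.

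End dates before onset then cannot occur, by construction. In the April example the imputed end becomes 30 April, a duration of 30 − 20 = 10 days against a true 7. The error is now toward longer durations, which is at least possible and easy to describe.

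The cost is SAP wording and programming. No data collection, sample size or primary analysis changes.
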